2.2.2.2 Subjects with CNS metastases

The presence or absence of CNS metastases (CNS mets) will be identified from the lesion locations (RECIST eCRF page) at baseline [REDACTED].

- Category ‘CNS mets present’: subjects whose lesion locations contain one or more of the following values (case insensitive)

BRAIN
BRAIN STEM
CEREBELLUM
CEREBRAL CORTEX
CEREBRUM
CERVICAL SPINE
CNS - NOT OTHERWISE SPECIFIED
CNS: SUPRATENTORIAL
CNS: INFRATENTORIAL
CORPUS CALLOSUM
FRONTAL
LEPTOMENINGEAL
LUMBAR SPINE
OCCIPITAL
PARIETAL
PITUITARY
PONS
SPINAL CORD
TEMPORAL
THALAMUS
THORACIC SPINE
WHOLE BRAIN

- Category ‘CNS mets absent’: will be assigned to all other subjects

For outputs based on the investigator assessment, identification of CNS metastases at baseline will use the data from the investigator review. For outputs based on the BIRC assessment, identification of CNS metastases at baseline will use the data from the BIRC review.

The number of subjects with CNS metastases in target lesions, non-target lesions, and new lesions as well as the responses on target lesions and non-target lesions will be summarized based on investigator and BIRC assessment, respectively.

The CNS metastases subgroups will be used for efficacy analyses of ORR, DOR and PFS.

Note: metastatic sites data collected in the Diagnosis and Extent of Cancer eCRF page will not contribute to the subgroup derivation.

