The best overall response for each subject is determined from the sequence of overall (lesion) responses according to the following rules:

- CR = at least two determinations of CR at least 4 weeks apart before the end of treatment.
- PR = at least two determinations of PR or better at least 4 weeks apart before the end of treatment (and not qualifying for a CR).
- SD = at least one SD assessment (or better) >7 weeks after start of treatment (and not qualifying for CR or PR).
- PD = progression ≤ 17 weeks after start of treatment (and not qualifying for CR, PR or SD).
- UNK = all other cases (i.e. not qualifying for confirmed CR or PR and without SD after more than 7 weeks or early progression within the first 17 weeks).

Subjects discontinuing from the study for PD must have it documented by radiologic evaluation. In cases of clinically-evident disease progression, all efforts should be made to perform a radiologic evaluation. Subjects with symptoms of rapidly progressing disease without radiologic evidence will not be classified as progression.

2.5.2.2 Statistical hypothesis, model, and method of analysis – Phase II Groups 1, 2, and 3

The Bayesian model employed for the primary analysis will not be repeated.

For the final CSR frequencies of the BOR categories will be presented and the response rate will be summarized using descriptive measures including 95% confidence intervals (CI) using the exact method [Clopper and Pearson 1934].

Individual lesion measurements and overall response at each assessment will be listed by group and subject.

2.5.2.3 Handling of missing values/censoring/discontinuations – Phase II Groups 1, 2, and 3

Subjects with unknown or missing BOR will be counted as failures. If there is no baseline tumor assessment, all post-baseline overall lesion responses are expected to be ‘Unknown’. If no valid post-baseline tumor assessments are available, the best overall response must be ‘Unknown’ unless progression is reported. For the computation of ORR, these subjects will be included in the FAS and will be counted as failures.

Censoring for new anti-cancer therapy

For BOR only tumor assessments performed before the start of any new anti-cancer therapy (including medication, radiotherapy and surgery) will be considered.

PFS will be censored at the date of the last adequate tumor assessment if no PFS event is observed prior to the analysis cut-off date or before the start of the new anti-cancer therapy date, whichever is earlier.

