2.7.1 Secondary endpoints

The secondary efficacy endpoints in Phase Ib and Phase II are BOR, ORR (if not already part of the primary analysis), disease control rate (DCR), duration of response (DOR), time to response (TTR), and progression-free survival (PFS). These endpoints are based on investigator assessment in accordance with RECIST 1.1. An additional endpoint is overall survival (OS).

For supportive analyses BOR, ORR, DCR, DOR, TTR, and PFS will also be evaluated based on the BIRC review of tumor data in accordance with RECIST 1.1. For Phase Ib data the independent review will only be performed for subjects from cohorts with the RP2D.

The secondary efficacy endpoints will be analyzed using the FAS.

Overall response rate and best overall response

See definitions in [Section 2.5.2.1](#).

Duration of response

DOR only applies to subjects whose best overall response is CR or PR according to RECIST 1.1 based on local investigators or BIRC review of tumor assessment data. The start date is the date of first documented response of CR or PR (i.e., the start date of response, not the date when response was confirmed), and the end date is defined as the date of the first documented progression or death due to any cause. Subjects continuing without progression or death will be censored at the date of their last adequate tumor assessment using the censoring rule described for the PFS analysis.

Disease control rate

DCR is defined as the proportion of subjects with a BOR of CR or PR, or SD according to RECIST 1.1 criteria.

Time to response

TTR is the time from date of first administration of study treatment to first documented response of CR or PR (which must be confirmed subsequently) using local investigators or BIRC review of tumor assessment data and according to RECIST 1.1. Subjects who did not achieve a confirmed PR or CR will be censored at:

- the maximum follow-up time (i.e. FPFV – LPLV used for the analysis in the respective subject group) for subjects who had a PFS event (i.e. either progressed or died due to any cause); [REDACTED]
- the last adequate tumor assessment date for all other subjects

Progression-free survival

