2.7.3 Handling of missing values/censoring/discontinuations

ORR

See [Section 2.5.2.3](#).

TTR

Subjects who did not achieve a confirmed PR or CR will be censored as described in [Section 2.7.1](#).

DOR

Subjects continuing without progression or death will be censored at the date of their last adequate tumor assessment using the censoring rule described for the PFS analysis.

PFS

PFS will be censored at the date of the last adequate tumor assessment if no PFS event is observed prior to the [REDACTED] analysis cut-off date or before the start of the new anti-cancer therapy date, whichever is earlier.

The date of last adequate tumor assessment is the date of the last tumor assessment with overall lesion response of CR, PR or SD before an event or a censoring reason occurred. In this case the last tumor evaluation date at that assessment will be used. If no post-baseline assessments are available (before an event or a censoring reason occurred) then the start date of treatment will be used.

In particular, PFS will be censored at the last adequate tumor assessment if one of the following occurs: absence of event; the event occurred after a new anti-cancer therapy was administered (see also [Section 2.5.2.3](#)); the event occurred after two or more missing tumor assessments.

The term ‘missing adequate tumor assessment’ is defined as a TA not performed or TA with overall lesion response of ‘UNK’. The rule to determine the number of missing TAs is based on the time interval between the date of last adequate tumor assessment and the date of an event. If the interval is greater than twice the protocol-specified interval between the TAs and 2 times the protocol-allowed time window around assessments, then the number of missing assessments will be 2 or more.

Refer to [Table 2-4](#) for censoring and event date options and outcomes for PFS.

Table 2-4 Outcome and event/censor dates for PFS analysis

Situation	Date	Outcome
No baseline assessment	Start date of treatment	Censored
Progression or death at or before next scheduled assessment	Date of progression (or death)	Progressed
Progression or death after exactly one missing assessment	Date of progression (or death)	Progressed
Progression or death after two or more missing assessments	Date of last adequate assessment prior to missed assessment	Censored
No progression (or death)	Date of last adequate assessment	Censored

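### 'CNS mets absent' is a residual category, so a subject with no baseline tumour assessment by the relevant reader is classed as CNS-negative and lowers the ORR in that subgroup

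*SAP*

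**What the plan says.** Section 2.2.2.2 names one data source: "The presence or absence of CNS metastases (CNS mets) will be identified from the lesion locations (RECIST eCRF page) at baseline" (a redaction follows). Subjects with at least one location from a fixed list are 'CNS mets present'. The other category, 'CNS mets absent', "will be assigned to all other subjects". Investigator outputs use the investigator's baseline lesions and BIRC outputs use the BIRC's. A note adds that "metastatic sites data collected in the Diagnosis and Extent of Cancer eCRF page will not contribute to the subgroup derivation". On use, it says: "The CNS metastases subgroups will be used for efficacy analyses of ORR, DOR and PFS".

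Other sections deal with subjects who lack a baseline tumour assessment:

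- **ORR, Section 2.5.2.3:** "If there is no baseline tumor assessment, all post-baseline overall lesion responses are expected to be" unknown, and "these subjects will be included in the FAS and will be counted as failures". Section 2.7.3 applies this to the secondary ORR analyses.
- **PFS, Table 2-4 in Section 2.7.3:** the row "No baseline assessment" gives censoring at the start of treatment.
- **DOR, Section 2.7.1:** "DOR only applies to subjects whose best overall response is CR or PR according to RECIST 1.1".
- **Analysis set, Table 2-2:** missing written consent is the only listed ground for exclusion from the FAS, so these subjects stay in.

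**The concern.** A residual category makes no distinction between a subject who was assessed and had no CNS lesion and a subject for whom there is nothing to read. The SAP expects that the second kind may occur and gives explicit rules for them in ORR and PFS, but its CNS rule does not set them apart.

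Its other subgroup factors are handled differently. T790M status has an unknown level (Section 2.2.2.1) and MET status a missing level when results are unavailable or insufficient (Section 2.11.5). The general convention in Section 2.1.3, that a missing category is shown where applicable, does not help: under the residual rule nobody is missing.

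What is at stake is the meaning of the 'absent' row in the ORR subgroup table. Every no-baseline subject enters it as an automatic non-responder, so the row mixes a response rate in CNS-negative subjects with a data-availability problem. The groups are small (a minimum of 40 in Group 3, Section 1.1.2), so a few subjects can move the estimate visibly.

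**Working it through.** The SAP gives no figure on this point, so there is nothing to reproduce. I followed a subject with no baseline tumour assessment through each endpoint and then sized the ORR effect with assumed counts.

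**Classification.** No baseline assessment means no lesion locations, hence no match to the CNS list, hence 'absent'. This is done per reader: a subject without a BIRC baseline is 'absent' in the BIRC outputs whatever the investigator recorded.

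**DOR.** Responses are expected to be unknown, so the subject has no CR or PR and does not enter DOR. No effect.

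**PFS.** The no-baseline row of Table 2-4 censors the subject at treatment start. The Kaplan-Meier estimate is the product over event times u of (1 − d_u/n_u), where n_u counts subjects with time ≥ u. A subject censored at treatment start has left before any later event time and is in no n_u, so the curve is unchanged. A numerical check that added 3 subjects censored at day 1 to 28 simulated subjects gave an identical curve. Only the subgroup N and the censoring counts change.

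**ORR.** The subject adds 0 to the numerator and 1 to the denominator. With r responders among N 'absent' subjects, k of whom have no baseline assessment:

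- as written: r / N
- with a separate level: r / (N − k)

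Assumed for illustration: N = 28 (out of a group of 40), r = 14 or 20, k = 1 to 4. Intervals are exact Clopper-Pearson 95%, the SAP's own method.

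| r | As written, r/28 | k | r/(28 − k) | Difference (points) |
|---|---|---|---|---|
| 14 | 50.0% (30.6–69.4) | 1 | 14/27 = 51.9% (31.9–71.3) | 1.9 |
| 14 | | 2 | 14/26 = 53.8% (33.4–73.4) | 3.8 |
| 14 | | 3 | 14/25 = 56.0% (34.9–75.6) | 6.0 |
| 14 | | 4 | 14/24 = 58.3% (36.6–77.9) | 8.3 |
| 20 | 71.4% (51.3–86.8) | 1 | 20/27 = 74.1% (53.7–88.9) | 2.6 |
| 20 | | 2 | 20/26 = 76.9% (56.4–91.0) | 5.5 |
| 20 | | 3 | 20/25 = 80.0% (59.3–93.2) | 8.6 |
| 20 | | 4 | 20/24 = 83.3% (62.6–95.3) | 11.9 |

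Whenever r > 0 the direction is fixed: the rule as written gives the lower ORR in 'absent'.

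**The case against.** **The visible text is incomplete.** A redaction follows directly after the data source in Section 2.2.2.2. Section 2.1.3 also points to Section 2.5.2.4 for subgroup definitions and analyses, and that section is not in the public text. A further condition could sit in either place. This calls for caution, but the residual rule that is visible carries no condition.

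**The effect is small and descriptive.** No test between the CNS subgroups is planned in the visible text. A shift of 2.6 points is minor beside an interval of 51.3–86.8%, and there may be no such subject. All of this stands, and it limits the weight of the point.

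**Taking failures out of a subgroup could flatter it.** They would not disappear: they stay in the FAS, count as failures in the group ORR, and appear under their own level.

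A reader might also infer more than the SAP supports:

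- *That subjects without brain imaging are hidden in 'absent' and so affect all three endpoints.* This depends on the baseline imaging schedule, which belongs to the protocol and is not shown. If brain imaging was mandatory, few or none are affected. The SAP offers no basis for a percentage.
- *That the no-baseline subjects narrow a CNS contrast in PFS or DOR.* They leave the PFS curve as it is and do not enter DOR. For ORR, 'narrow' would require the 'absent' subgroup to have the higher rate, which the SAP does not state.
- *That ignoring the Diagnosis page is an error.* It is a disclosed choice and fits a design in which each reader's outputs rest on that reader's lesions. Section 2.3.1 still summarises the metastatic sites from that page.
- *That 'absent' means proven negative.* The SAP makes no such claim.

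**Conclusion.** The point holds in a limited form. Followed as written, Section 2.2.2.2 labels as CNS-negative any subject without a baseline tumour assessment by the relevant reader, and such a subject lowers the descriptive ORR of the 'absent' subgroup. In the illustration the reduction is about 2 to 12 points for 1 to 4 subjects among 28; for the single-subject case it is 74.1% against 71.4%.

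This rests on assumed counts, because the SAP does not say how many such subjects there are and the number may be zero. It also takes the redacted text to contain no exception and the no-baseline row of Table 2-4 to govern PFS for these subjects. The group-level ORR, the PFS curve and DOR are not affected.

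**What to change.** In Section 2.2.2.2, replace the residual definition by three levels, applied separately for investigator and BIRC outputs:

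- **CNS mets present:** as now.
- **CNS mets absent:** a baseline tumour assessment by that reader exists and lists no CNS location.
- **CNS status not assessable:** no baseline tumour assessment by that reader.

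Report the number in the third level in each ORR and PFS subgroup output. These subjects remain in the FAS and remain failures in the group ORR.

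The cost is a change of SAP wording and one derivation from data already collected; the downside is a slightly smaller 'absent' subgroup. A cross-tabulation of RECIST-derived CNS status against the Diagnosis-page sites would be informative but is optional.

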2.2.2.3 Analyses by subgroup

Analyses by subgroups are described in the respective efficacy analysis and biomarker analysis sections. No safety subgroup analyses are planned.

2.3 Subject disposition, demographics and other baseline characteristics

The FAS will be used for all baseline and demographic summaries and listings unless otherwise specified. Summaries will be reported by treatment group and for all subjects and listings will be reported by treatment group to assess baseline comparability. No inferential statistics will be provided. Data will be listed individually by subject.

2.3.1 Basic demographic and background data

All demographic and baseline disease characteristics data will be summarized and listed by treatment group. Categorical data (e.g. gender, age groups: <65, ≥ 65–<85, ≥ 85 years, race, ethnicity, ECOG performance status) will be summarized by frequency counts and percentages; the number and percentage of subjects with missing data will be provided. Continuous data (e.g. age, baseline weight, height, body mass index) will be summarized by descriptive statistics (N, mean, median, standard deviation, minimum, maximum, 25th and 75th percentile). BMI (kg/m²) will be calculated as weight [kg] / (height [m]²) using weight at baseline.

Diagnosis and extent of cancer

Summary statistics will be tabulated for diagnosis and extent of cancer. This analysis will include the following: primary site of cancer, details of tumor histology/cytology, histological grade, stage at time of initial diagnosis, stage at time of study entry, time (in months) from initial diagnosis of primary site to start of study treatment, time since most recent relapse/progression to start of study treatment (in months), time from initial diagnosis to first recurrence/progression (in months), presence/absence of target and non-target lesions at baseline, number and type of metastatic sites involved.

Note: Presence/absence of target and non-target lesions will be based on the data collected on RECIST target/non-target lesion assessment eCRF pages. Metastatic sites will be based on the Diagnosis and extent of cancer eCRF page. [REDACTED]

2.3.2 Medical history

Medical history and ongoing conditions, including cancer-related conditions and symptoms entered on the eCRF will be summarized and listed by treatment group. The summaries will be presented by primary system organ class (SOC), preferred term (PT) and treatment group. Medical history and current medical conditions will be coded using the Medical Dictionary for Regulatory Activities (MedDRA) terminology. The MedDRA version used for reporting will be specified in the CSR and as a footnote in the applicable tables/listings.

Other

Not all data collected at baseline will be listed again. The corresponding listings were provided in the [\[Primary CSR\]](#).

2.3.3 Subject disposition

The number (%) of subjects in the FAS who discontinued the study phases and the reason for discontinuation will be presented overall and by treatment group.

The following summaries will be provided with percentages based on the total number of FAS subjects:

Study treatment phase

- Number (%) of subjects who are still on-treatment at the time of the data cut-off date for the analysis (based on the 'End of Treatment Disposition' eCRF not completed; for the final analysis the number is expected to be zero and will not be presented)
- Number (%) of subjects who discontinued the study treatment phase (based on the 'End of Treatment Disposition' eCRF)
- Primary reason for study treatment phase discontinuation (based on the discontinuation reason entered in the 'End of Treatment Disposition' eCRF)

Post-treatment follow-up phase for subjects who discontinued the treatment phase

- Number (%) of subjects who did not enter the post-treatment follow-up
- Number (%) of subjects who entered the post-treatment follow-up and are still ongoing at the time of the data cut-off date for the analysis (based on the 'End of Post Treatment Phase Disposition' eCRF; for the final analysis the number is expected to be zero and will not be presented)
- Number (%) of subjects who entered the post-treatment follow-up and have discontinued
- Primary reason for discontinuation from the post-treatment phase

Survival follow-up phase

- Number (%) of subjects who did not enter the survival follow-up (based on the 'End of Treatment Phase' or 'End of Post-treatment follow-up' page)
- Number (%) of subjects who entered the survival follow-up and are ongoing (based on the 'End of Treatment Phase' or 'End of Post-treatment follow-up' page and the 'Survival information' page)
- Number (%) of subjects who entered the survival follow-up and discontinued (based on the 'End of Treatment Phase' or 'End of Post-treatment follow-up' page and the 'Survival information' or 'Death' page)

A listing of study completion by treatment group for Phase Ib and Phase II will be produced separately using the FAS.

Protocol deviations

The number (%) of subjects in the FAS with any protocol deviation will be tabulated by deviation category and deviation (as specified in the study Data Handling Plan) overall and by treatment group. All protocol deviations will be listed.

An additional table and listing will be provided to summarize and list, respectively, deviations related to the Covid-19 pandemic. A cross-tabulation of COVID-19 related PD vs. relationship will also be prepared.

Analysis sets

The number (%) of subjects in each analysis set (defined in [Section 2.2](#)) will be summarized by treatment group using the FAS as denominator. In addition, subjects excluded and reasons for exclusion from each analysis set will be listed.

2.4 Treatments (study treatment, concomitant therapies, compliance)

2.4.1 Study treatment / compliance

Duration of exposure, actual cumulative dose, dose intensity (DI) and relative dose intensity (RDI) will be summarized by treatment group, separately for each component of study treatment. Duration of exposure will also be presented for the study treatment. Duration of exposure will be categorized into time intervals; frequency counts and percentages will be presented for the number of subjects in each interval. The number (%) of subjects who have dose reductions or interruptions, and the reasons, will be summarized by treatment group.

Subject level listings of all doses administered on treatment along with dose change reasons will be produced.

The safety set will be used for all summaries and listings of study treatment.

Duration of exposure to study treatment

Duration of exposure to study treatment is considered by taking into account the duration of exposure to the investigational drugs:

Duration of exposure to study treatment (days) = (last date of exposure to study treatment) – (date of first administration of study treatment) + 1.

The last date of exposure to study treatment is the latest of the last dates of exposure to any of the investigational drugs (see [Section 2.1.4](#)).

Summary of duration of exposure to study treatment will include categorical summaries and continuous summaries (i.e. mean, standard deviation etc.) using the time unit weeks. The following time intervals will be presented: ≤ 4 weeks, $4 < \leq 8$ weeks, $8 < \leq 12$ weeks, $12 < \leq 16$ weeks, $16 < \leq 24$ weeks, $24 < \leq 32$ weeks, $32 < \leq 52$ weeks, $52 < \leq 78$ weeks and >78 weeks.

Duration of exposure to investigational drugs

Duration of exposure to investigational drug (days) = (last date of exposure to investigational drug) – (date of first administration of investigational drug) + 1.

The last date of investigational drug exposure is defined as the date of last administration of a non-zero dose of the drug (see [Section 2.1.4](#)).

For subjects who did not take any drug, the duration of drug exposure is by definition equal to zero.

The exposure duration may include periods of temporary interruption. If a subject is still on treatment at the time of data cut-off, the end date of investigational drug/study treatment will be replaced by the data cut-off date and the above calculations will be applied.

Summary of duration of exposure of investigational drug (INC280, EGF816) will include categorical summaries (based on the same time intervals as for study treatment) and continuous summaries (i.e. mean, standard deviation etc., with time unit day).

Cumulative dose

Cumulative dose of study treatment is defined as the total dose given during the study treatment exposure and will be summarized for each of the study treatment components (INC280 and EGF816, respectively).

The *planned cumulative dose* for a study treatment component (INC280 or EGF816) refers to the total planned dose as per the protocol up to the last date of investigational drug administration. The planned cumulative dose will not be summarized or listed. It will be used for relative dose intensity calculations.

The *actual cumulative dose* refers to the total actual dose administered, over the duration for which the subject is on the study treatment as documented in the DAR eCRF.

For subjects in the Safety Set who did not take one component of study treatment the cumulative dose for that component is by definition equal to zero.

For continuous dosing, the actual cumulative dose is the sum of the non-zero doses recorded over the dosing period and the planned cumulative dose is the planned starting dose summed over the same dosing period.

Dose intensity and relative dose intensity

Dose intensity (DI) for subjects with non-zero duration of exposure is defined as follows for each of the study treatment components (INC280, EGF816):

$$\text{DI (mg/day)} = \text{actual cumulative dose (mg)} / \text{duration of exposure (days)}.$$

For subjects who did not take any drug the DI is by definition equal to zero.

Planned dose intensity (PDI) is defined as follows:

$$\text{PDI (mg/day)} = \text{planned cumulative dose (mg)} / \text{duration of exposure (days)}.$$

Relative dose intensity (RDI) is defined as follows:

$$\text{RDI} = \text{DI (mg/day)} / \text{PDI (mg/day)}.$$

DI and RDI will be summarized separately for each of the study treatment components, using the duration of exposure of each of the components. The summary of RDI includes categorical summaries for RDI expressed as percentage for the following intervals: $\leq 75\%$, $>75\text{--}90\%$, $>90\text{--}110\%$, $\geq 110\%$.

Dose reductions, interruptions or permanent discontinuations

The number of subjects who have dose reductions, permanent discontinuations or interruptions, and the reasons, will be summarized separately for each of the study treatment components (INC280, EGF816).

‘Dose interrupted’ and ‘Dose permanently discontinued’ fields from the DAR eCRF together with the dose taken will be used to derive the dose reductions, dose interruptions, and permanent discontinuations, respectively.

The corresponding field ‘Reason for dose change/dose interrupted’ will be used to summarize the reasons.

A dose change is either ‘change in prescribed dose level’ or ‘dosing error’ where actual dose administered/total daily dose is different from the prescribed dose.

For the purpose of summarizing interruptions and reasons, in case multiple entries for interruption are entered on consecutive days with different reasons they will be counted as separate interruptions. However, if the reason is the same in these mentioned multiple entries on consecutive days, then it will be counted as one interruption.

Interruption: To derive dose interruptions at the end of the treatment period or around the date of the cut-off, the following rules will be used.

- A dose interruption followed by a permanent discontinuation will be counted as permanent discontinuation, not as interruption.
- A dose interruption which is ongoing at the time of the data cut-off is not expected for the final analysis; such cases will be considered as a permanent discontinuation.

Reduction: A dose change where the prescribed dose level is lower than the previous prescribed dose level or where the actual dose administered/total daily dose is lower than the calculated dose amount based on the prescribed dose. Therefore any dose change to correct a dosing error will not be considered a dose reduction. Only dose change is collected in the CRF, number of reductions will be derived programmatically based on the change and the direction of the change.

